8.4 Safety Monitoring

8.4.1 Physical and Neurological Examinations

Physical and neurological examinations will be performed at the Screening Visit, Baseline Visit, Visit 12, EOT Visit, and the Follow-up Visit.

8.4.2 Electrocardiograms (ECG)

For each participant, an ECG will be conducted at the Screening Visit, Visit 12 and EOT Visit. The ECG will be conducted by qualified study personnel, and be interpreted by a qualified physician or other designated qualified medical personnel as soon as possible after the administration.

8.4.3 Vital Signs

Vital signs including blood pressure, heart rate, temperature and respirations will be measured at all athome and in-clinic visits. Blood pressure and pulse should be measured with participant in sitting position for at least 5 minutes. Height will be measured at screening. Body weight will also be measured according to the schedule of events table in protocol section 2.

8.4.4 Additional Safety Assessments

C-SSRS

Consistent with FDA regulatory guidance, any occurrence of suicide related thoughts or behaviors will be assessed per the Schedule of Events (Section 2). The C-SSRS is an instrument that collects the occurrence, severity and frequency of suicide related thoughts or behaviors. The "Baseline" version will be used for the initial screening, and the "Since Last Visit" when assessed shall be used at following visits, when scheduled for administration.

Geriatric Depression Scale (GDS)

The GDS is a simple 30-item measure used to identify depression in elderly individuals. The simplicity of the GDS (questions are answered only by "yes" or "no") enables the scale to be used with ill or moderately cognitively impaired individuals. One point is assigned to each answer and the cumulative score is rated on a scoring grid. The grid sets a range of 0 to 9 as 'normal', 10 to 19 as 'mildly depressed', and 20 to 30 as 'severely depressed'.

Generalized Anxiety Disorder (GAD)-7

The GAD-7 is a simple seven item questionnaire used to identify anxiety levels in individuals. The GAD-7 is calculated by assigning scores of 0, 1, 2, and 3, to the response categories of "not at all," "several days," "more than half the days," and "nearly every day," respectively. GAD-7 total score for the seven items ranges from 0 to 21. Scores of 5, 10, and 15 represent cut-points for mild, moderate, and severe anxiety, respectively. Though designed primarily as a screening and severity measure for generalized anxiety disorder, the GAD-7 also has moderately good operating characteristics for three other common anxiety disorders: panic disorder, social anxiety disorder, and post-traumatic stress disorder.

8.4.5 Adverse Event(s), Serious Adverse Events and Monitoring

The principal investigator is responsible for monitoring the safety of participants in the trial, and, with medically qualified sub-Investigators, will oversee and document any event that seems unusual, and document the review of each laboratory safety report. The investigators are responsible for the follow-up for all AEs that are considered serious or otherwise medically important, considered related to the investigational product or procedures in the trial, or that caused the participant to discontinue the investigational product before the recognized end of study treatment. The frequency of follow-up evaluations is at the discretion of the investigator.

After the informed consent is signed, designated study staff will document and report the occurrence and nature of any new medical conditions or events since the informed consent signing as an adverse event. For each AE, the investigator will evaluate relatedness to study participation, severity, and expectedness, taking into account issues including AD pathology, concomitant treatments, and medical history.

A safety medical monitor will advise and consult with the Sponsor, PI, sub-Investigator(s) and study staff on the following matters: Review protocol halting rules; Advise protocol team on safety oversight; Evaluate adverse events/SAEs and reviews safety reports once quarterly or more often if deemed necessary. This individual will be independent of the study team, and properly credentialed.

As a note: If a participant receives two injections in one day, the study team will report this as a protocol deviation. If the team learns of this at the time of the injections, the participant will be instructed to skip the dose on the following day. As determined by [name]., hematologist and SESAD lead Medical Sub-I, in consideration of the phase 1 trial that administered sargramostim at 16 times the recommended dosage without causing harm, instances of two doses in one day for this trial does not constitute patient harm.

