5.1.2 Justification for Dose

Recombinant human GM-CSF (Leukine®/sargramostim) is currently marketed in the U.S. by Partner Therapeutics. Leukine® has been FDA-approved since 1991 and safely used worldwide for leukopenia, in multiple stem cell transplantation settings, and following induction chemotherapy in patients 55 years and older with acute myelogenous leukemia (AML) to shorten time to neutrophil recovery and to reduce the incidence of severe and life-threatening infections. Specifically, sargramostim is a leukocyte growth factor indicated for use following induction chemotherapy in AML, for use in mobilization and following transplantation of autologous peripheral blood progenitor cells, for use in myeloid reconstitution after autologous bone marrow transplantation, for use in myeloid reconstitution after allogeneic bone marrow transplantation, and for use in bone marrow transplantation failure or engraftment delay (104, attached as Appendix E). The FDA-approved recommended dosage is 250 µg/m²/day SC for up to 42 days or until absolute neutrophil count (ANC) reaches 1,500 cells/mm³ for three consecutive days. Although it is not possible to directly translate the dosage used in mice to that to be used in humans for cognitive enhancement, the dosage of GM-CSF administered to transgenic AD mice that resulted in cognitive improvement and amyloid plaque reduction was about twice the recommended dosage of sargramostim $(\sim 500 \mu g/m^2/day SC or \sim 167 \mu g/kg/day)$ for a total of 20 injections (cumulative amount per mouse = 100) μg). However, several clinical trials with sargramostim have shown no serious AEs at dosages of >500 μg/m²/day ¹⁰⁵⁻¹⁰⁷, and the maximum amount of sargramostim that can safely be administered by single or multiple dose has yet to be determined. Doses up to 100 µg/kg/day (4,000 µg/m²/day or 16 times the

recommended dose) were administered to four patients in a Phase I uncontrolled study by continuous intravenous infusion for 7 to 18 days and with WBC reaching up to 200,000 cells/mm³. All AEs (dyspnea, malaise, nausea, fever, rash, sinus tachycardia, headache and chills) were reversible upon discontinuation of the drug, as discussed above (¹⁰⁴, attached as Appendix E). These and other results, from the approximately 470,000 patients that have received sargramostim during its post-marketing setting (¹⁰³; attached as Appendix D), indicate that sargramostim has an extremely good safety profile.

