Notably, the Moffitt Cancer Center study, described in the Preliminary Clinical Results section above, used the recommended FDA-approved dosage (250 $\mu g/m^2/day$ SC) and found highly significant (p < 0.01) cognitive enhancement in patients treated with GM-CSF plus G-CSF compared to those treated with G-CSF alone (70 , attached as Appendix C). And, most importantly, in the recently completed pilot safety and efficacy trial (described above, NCT01409915) in which sargramostim (250 $\mu g/m^2/day$ SC) was administered to mild-to-moderate AD participants for 15 days over a 19-day period, the randomized participants have completed the trial with no drug-related serious AEs, including no evidence of ARIAs. Therefore, randomized participants will be started at the full FDA-approved recommended sargramostim dose.

During the course of this clinical investigation, the study team has determined that full dosing at 250 $\mu g/m^2/day$ SC for the full 6 month treatment period of the study may have unknown risks related to immune functioning of participants, and the decision was made to change the dosing schedule from all 24 weeks at 250 $\mu g/m^2/day$ SC five days a week, to 178.57 $\mu g/m^2/day$ SC seven days a week. This maintains total weekly dosing while reducing total daily dosing.

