7.4 Dosage Modification

Note: As the safety of the participant is paramount, the participants and their study partners will be told at the time of the informed consent that the study team will be monitoring their health and well-being through review of adverse events, laboratory results, and examinations performed during the trial. To help minimize the possibility of any unblinding of participants or study partners within any of these scenarios listed below, all participants will be informed at their time of consent that they may be asked to do one of three things if they are having adverse effects or abnormal laboratory results including: stopping treatment; receiving new, replacement syringes; or continuing treatment with the same syringes. Additionally, they will be told that the study team will continuously monitor their lab results, but they may not be told their specific results. Additionally, they will be informed that the trial physician or clinician designee will take the opportunity to examine them for clinical condition as a general safety measure if they are ever instructed to return to the CU-AMC site for an unscheduled visit.

The greatest safety concern noted with the investigational product is excessive leukocytosis. As advised by the product safety instructions, a CBC with differential, including examination for the presence of blast cells, will be competed twice weekly during the 24-week-long treatment phase. Additionally the product insert states that "If the ANC exceeds 20,000 cells/mm³ or if the platelet count exceeds 500,000/mm³, LEUKINE administration should be interrupted or the dose reduced by half. The decision to reduce the dose or interrupt treatment should be based on the clinical condition of the patient." If a participant has CBC with differential results which indicate that their ANC has exceeded 20,000 cells/mm³, their white blood cell count has exceeded 50,000 cells/mm³, or their platelet count has exceeded 500,000/mm³, the participant and the study partner will be immediately contacted, asked whether the participant is experiencing any adverse health effects, AND instructed NOT to administer any additional study product

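### Section 8.4.5 rules in advance that two doses in one day do no harm, citing a 16-fold-dose study for which section 5.1.2 reports adverse events and WBC up to 200,000 cells/mm³

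*Protocol*

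**What the plan says.** Section 8.4.5 deals with accidental double dosing in a closing note: "If a participant receives two injections in one day, the study team will report this as a protocol deviation". The note then records a determination by the lead medical sub-investigator, a hematologist. Its single stated reason is a phase 1 trial that gave sargramostim at "16 times the recommended dosage without causing harm, instances of two doses in one day for this trial does not constitute patient harm". No reference is given for that trial.

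Section 5.1.2 describes a phase 1 study at the same multiple, with doses up to 4,000 µg/m²/day. It had no control group and only four patients, who received the drug through a vein without interruption. Treatment is said to have run "for 7 to 18 days and with WBC reaching up to 200,000 cells/mm³". On tolerability, the section goes on to report: "All AEs (dyspnea, malaise, nausea, fever, rash, sinus tachycardia, headache and chills) were reversible upon discontinuation of the drug". The same section states that the largest amount that can safely be given, as one dose or several, is not yet known.

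Two other places show how the protocol regards a raised white cell count. Section 7.4 names excessive leukocytosis as the chief safety concern with the product and has dosing interrupted when a CBC shows, among other triggers, that "their white blood cell count has exceeded 50,000" cells/mm³. Section 8.4.5.3 lists an excessive rise in white cells, and also shortness of breath, among the less common but potentially serious effects.

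**The concern.** A study with dyspnea, fever, rash and sinus tachycardia among its adverse events, and a peak white cell count well above this trial's own interruption level, is cited in another section as having caused no harm. That description is then the sole stated support for a general ruling on every future double dose.

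The ruling matters because long-term safety and tolerability are the primary objective, and section 9.2.1 compares adverse event toxicity grades between arms. Study partners give the injections at home from a weekly supply of syringes, so double doses are foreseeable, and the protocol plans for them. Section 8.4.5 otherwise asks the investigator to judge relatedness, severity and expectedness for each adverse event. A standing statement that the exposure is harmless anticipates that judgement. Taken literally, it would misclassify any double dose that did cause harm.

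**Working it through.** No sample size, power or error-rate figure is involved. The check is a comparison of text with some direct arithmetic.

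**1. Is it the same study?** Section 5.1.2 gives 4,000 µg/m²/day for the high-dose study and 250 µg/m²/day as the recommended dose. 4,000/250 = 16.0, which reproduces the stated multiple. The phase also matches, and the protocol describes no other study at that multiple. The identification is an inference, because section 8.4.5 cites no source.

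**2. The two descriptions side by side.**
- Section 8.4.5: phase 1, 16-fold dose, no harm.
- Section 5.1.2: phase 1, 16-fold dose, four patients, uncontrolled, continuous intravenous infusion, 7 to 18 days. Dyspnea, malaise, nausea, fever, rash, sinus tachycardia, headache and chills were reported, all reversible on discontinuation. WBC reached 200,000 cells/mm³.

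Reversible events are events that occurred. The first description would fit the second only if harm meant lasting harm, and section 8.4.5 does not say so.

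**3. White cell count against the trial's own threshold.** 200,000/50,000 = 4.0. The cited study reached four times the WBC at which section 7.4 interrupts treatment.

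**4. Size of the exposure at issue.** Two daily doses are 2 × 178.57 = 357.14 µg/m². Relative to the cited study, 357.14/4,000 = 0.089, or about 9% of one day's dose there. The route differs too: subcutaneous injection here, intravenous infusion there.

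**5. What four patients can exclude.** The protocol does not say how many of the four had each event. For an event seen in none of them, the exact upper confidence limit on its true rate is:
- one-sided 95%: 1 − 0.05^(1/4) = 52.7%;
- two-sided 95%: 1 − 0.025^(1/4) = 60.2%.

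An event with a true rate of 20% would be missed in all four with probability (1 − 0.20)^4 = 0.41. Even an event-free series of four would therefore be weak support for a categorical statement, and this series was not event-free.

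**The case against.** **Reversibility.** All the adverse events were reversible, so the phrase in section 8.4.5 may be shorthand for no lasting harm. That is a plausible account of what was meant, but the ruling is categorical and carries no such qualification.

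**Existing safeguards.** A reader might infer that a double dose is recorded as a deviation and nothing else, so that related adverse events drop out and the primary safety record is biased. The text does not support this. Section 8.4.5 calls for a deviation report without excluding anything further. It also requires any new condition or event after consent to be documented and assessed. Section 8.4.5.1 requires a seriousness assessment of every adverse event, and section 8.4.5.3 sends non-serious events to the DSMB in aggregate. Twice-weekly CBCs and the section 7.4 thresholds apply whatever the cause. Under-recording is conjecture.

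**The dose change.** Two doses come to 357.14/250 = 1.43 times the earlier daily dose, which section 5.1.2 says "may have unknown risks related to immune functioning of participants". It is tempting to call this a second contradiction. It is not one, because that rationale concerns dosing over the full six-month treatment period, and one double dose is a different exposure. When staff learn of it at the time, the note has the next day's dose skipped, so the two-day total stays at 357.14 µg/m².

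**Relevance of the high-dose findings.** The WBC peak followed far larger doses by continuous infusion, and section 5.1.2 also mentions several trials without serious adverse events above 500 µg/m²/day, which exceeds a double dose. Both points stand against any claim that a double dose is dangerous. Neither repairs the stated justification: section 8.4.5 does not rely on those other trials, and an absence of serious events is narrower than an absence of harm.

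**Clinical judgement.** Whether a given double dose harmed a participant is a clinical matter. That favours deciding it case by case over a general ruling made in advance.

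**Conclusion.** The concern holds as an internal inconsistency. The protocol's own account of the apparent source study does not support the advance ruling in section 8.4.5, and the statement in section 5.1.2 that the maximum safe dose is undetermined sits badly with a categorical conclusion. The basis is four uncontrolled patients treated by another route, with eight kinds of adverse event and a WBC peak four times this trial's interruption level.

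The point goes no further than that. It discredits the stated reason for the ruling; it does not show that a double dose is harmful, and the documents give no ground for saying that the safety record will be distorted. The conclusion rests on one assumption: that the trial cited in section 8.4.5 is the one described in section 5.1.2. If it is a different study, the protocol neither identifies nor describes it, and the ruling has no support that a reader can check.

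**What to change.** Reconcile sections 8.4.5 and 5.1.2 so that the 16-fold-dose study is identified and described consistently, taking account of how sections 7.4 and 8.4.5.3 treat leukocytosis. Replace the blanket determination in section 8.4.5 with a statement that each double dose is reported as a deviation and that any harm is assessed case by case under the adverse event rules already in that section. Make double doses identifiable in the safety data and list them in the DSMB aggregate report.

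The cost is a few sentences and one flag on existing forms, with minor extra recording. No visits or tests are added. No view is taken on the dose or on the instruction to skip the following day's injection.

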8.4.5.1 Serious Adverse Events

A serious adverse event, in relation to this clinical trial, is defined as something that results in:

- death.
- initial or prolonged inpatient hospitalization.
- a life-threatening event.
- persistent or significant disability.
- congenital birth defect.
- important medical events that might not be immediately life-threatening, or result in hospitalization, or death, but may require intervention to prevent such, including serious allergic reaction.

All AEs since the signing of the informed consent are to be assessed for seriousness, documented, and, if a serious adverse event, reported to the Sponsor within 24 hours of becoming known to the principal

investigator or qualified sub-Investigator. As well, the Data Safety Monitoring Board will monitor reported AEs and SAEs as a part of their role overseeing the protection of human participants.

8.4.5.2 Protection of Participants

Because of the extensive safety history of sargramostim in elderly patients, serious safety issues are not anticipated, however, vigilance in assessing safety is required. A review of published AEs for GM-CSF and the Leukine[®] Product Insert and the papers it references will be used to guide the safety monitoring protocol (attached as Appendix E). The greatest safety concern noted with sargramostim is excessive leukocytosis. Therefore, as advised by the product insert, a CBC with differential, including analysis for blast cells, will be conducted at two time-points every week during the 24- week-long treatment phase. Refer to section 7.4 for details on dosage modification guidelines. In addition, the DSMB (described below) will monitor laboratory results, the MRI studies, and the cognitive assessments for any indications of toxicity. Following are the abbreviated categories of the National Cancer Institute's (NCI) graded toxicity protocol used by Daud et al., (2008) for assessing safety of Leukine^{® 123}, although the latest version of the NCI-CTCAE (Version 5.00: November 27, 2017) will also be referenced for all AEs (attached as Appendix F):

Anemia
Lymphopenia
Pain
Fever
Flu-like symptoms
Arthralgia/myalgia
Injection-site reaction
Fatigue
Abdominal cramps
GERD/indigestion
Insomnia
Cough
Sweating

Full description of the DSMB will be provided in the charter. The DSMB will be comprised of members of relevant disciplines to overseeing conduct of a clinical trial for AD. The DSMB will be charged with overseeing participant safety. An initial meeting of the DSMB will be held before enrollment occurs in order for the members to review the study protocol and the study/participant termination guidelines. The DSMB will be required to meet at a minimum of one time per year. Data will be reviewed according to the DSMB mandated timeframe if a treatment related serious AE (SAE) or serious unexpected AE (SUAE) is reported. As mentioned above, SAEs and SUAEs will be reported per DSMB timeframes to the DSMB to discuss the SAEs/SUAEs and to decide whether the study should continue. Of note, if SAEs of Grade 3 or 4 occur in 20% of the initial 14 participants following sargramostim (or placebo) administration, the study will be halted while the Sponsor consults with the DSMB for final determination of study status. On the other hand, if the trial data indeed demonstrate clear safety and positive efficacy results from administration of sargramostim into AD participants at the end of the trial analyses, the DSMB may ethically consider and provide recommendations for open label extension study for trial participants, in which case the Sponsor will seek guidance from COMIRB and the FDA regarding how to proceed with these recommendations. All DSMB meetings will be documented and submitted to SARC. Once chartered, the DSMB membership will be listed in Appendix I.

8.4.5.3 Data Monitoring Plan: Data Recording:

These functions will be carried out by the study staff and transcribed into the case report forms (adverse events page). The principal investigator or qualified medical designee will review, edit, and sign off on the AE form, and the AE form filed by the PI or designated staff. Laboratory results and data from case report forms will be entered into a computerized data registry.

Data Verification: The PI or designated qualified sub-Investigator will discuss the AEs with the study coordinator(s), and will verify AE data entry.

Data to be monitored, assessed, and reported to/by the DSMB: (From Product insert)

Below is a list of possible data to be monitored, assessed and potentially reported to the DSMB. This list is not exhaustive, but comprised of information found in other studies of the investigational product.

Common but non-life threatening side effects include:

- Fatigue or asthenia
- Malaise
- Rash
- Itching (pruritus)
- Vomiting
- Diarrhea
- Abdominal pain
- Sore throat (pharyngitis)
- Chills
- Bone pains
- Joint pains
- Weight loss or gain
- Elevations in kidney or liver enzymes
- Fluid retention (peripheral edema)
- Injection site irritation
- Insomnia
- Headaches
- Transient Fevers

Less common but potentially serious side effects include:

- Bleeding into the eye
- Allergic reactions
- Excessive increase in white blood cell count
- Fluid retention in the lung lining (pleura) and in the heart lining (pericardium)
- Shortness of breath
- Occasional transient heart rhythm changes (supraventricular tachycardia)
- Sweating, tachycardia, claustrophobia, or anxiety induced by the MRI procedure

Potential side effects of unknown frequency:

- Leukopenia (low white blood cell count)
- Neutropenia (low neutrophil count)

Adverse event of special interest (AESI) include:

An AESI is an AE (serious or non-serious) of scientific and medical concern specific to the program, for

which ongoing monitoring and immediate notification to the DSMB is required. Such events may require further investigation in order to characterize and understand them. Adverse events of special interest may be added or removed during a study by protocol amendment.

- ADA
- Acute hypersensitivity/anaphylaxis
- Leukopenia (low white blood cell count)
- Neutropenia (low neutrophil count)

Report of Unexpected Problems to the DSMB: The study coordinator will notify the PI or qualified sub-Investigator of any unexpected problems. The PI will contact the chair of the **DSMB** when unexpected problems arise that require immediate action.

Criteria for Action:

Specific triggers that will dictate when a specified action (such as reporting or stopping) is required. Any SAE or unexpected problem that meets the COMIRB criteria of reporting will be reported per COMIRB guidelines. Any serious AEs meeting the FDA reporting criteria, the FDA will also be notified according to their reporting guidelines.

Stopping rules:

Study: If treatment related serious AEs (SAEs) of Grade 3 or 4 occur in 20% of participants following sargramostim administration, the study will be stopped (Appendix F).

Participant: For individual participants, the **PI or Sub-I** may discontinue any participant if they reach grade 3 or 4 in any category, if laboratory results indicate blast cell appearance, or if they worsen in any of the cognitive tests by more than two standard deviations than would be normally expected from someone at their baseline measurements, or if they have any values that have exceeded greater than two times upper limits of normal for any trial measures. Participants are, of course, free to withdraw from the study at any time for any or no reason.

Specific participant stopping criteria for Absolute Neutrophil (ANC) count values are as follows:

• If a participants Absolute Neutrophil Count (ANC) is less than 0.5x10E3/uL (500 cells per microliter) at any CBC with differential safety blood draw post randomization, the participant will be monitored for potential infections over the course of 1 week until another CBC with differential is completed. If the ANC value does not demonstrate improvement (returned to a value above 0.5x10E3/uL), administration of the study drug to the participant should be discontinued.

Participants will be followed-up according to the study procedures as specified in this protocol up to the scheduled date of study completion, or up to recovery or stabilization of any AE to be followed-up as specified in this protocol, whichever comes last. If possible, and after the permanent discontinuation of treatment, the participants will be assessed using the procedures normally planned for the EOT visit with the treatment/placebo, including, but not limited to, LP (if chosen), imaging assessments and cognitive assessments. All cases of permanent treatment discontinuation should be recorded after confirmation.

The PI may also determine that a trial participant should no longer remain in the trial if there is evidence of uncontrolled hypertension. For an individual who has consented to volunteer for the trial, meets inclusion criteria and is enrolled, then begins the treatment phase of the trial, but who subsequently is determined to exhibit uncontrolled hypertension for more than 2 weeks (14 treatment days), the DSMB will be notified, within accepted timeframe, adverse events reporting protocols will be followed, and the following criteria will be used to determine whether the participant needs to be removed from the trial:

Inclusion Screening Criteria for hypertension:

• The screening BP will be no greater than 160 systolic or 95 diastolic. If the initial BP reading is greater than 160 systolic or 95 diastolic, the BP will be measured in triplicate over the course of the visit, with the average BP calculated. (This limit will apply to all and any BP measurements during the screening process.)

Management Criteria during the treatment phase of the study:

- Should blood pressure rise above 165 systolic or 95 diastolic, indicating uncontrolled hypertension, the participant will have treatment interrupted and may be removed from the study. Determination of uncontrolled hypertension will be assessed through taking of BP in triplicate during the visit in which the average criteria of greater than 165 systolic or 95 diastolic is noted.
- If the participant displays symptoms related to, or meets clinical criteria of, hypertensive urgency or emergency, treatment will be interrupted and the participant referred to emergency services by the PI, clinical sub-Investigator or other qualified designee.
- The participant's hypertensive regimen may be adjusted by the primary care provider during the study as needed.
- If any participant, who has been interrupted from treatment for uncontrolled hypertension and depending upon the period of time taken for their BP to be controlled below 160 systolic or 95 diastolic, the trial physician, in consultation with the Sponsor, may decide for re-initiation of treatment (see Section 7.5 Interruption of Treatment).

Reporting:

Timeframe for reporting: Any Grade 2 AEs and abnormal Grade 2 laboratory results, including CBC with differential results, which require temporary interruption of treatment (Sections 7.4 - 7.5), will be reported to the **DSMB** for review within the standard DSMB aggregate report. Serious AEs (SAE) and unexpected SAEs related to the trial will be reported within five business days to the **DSMB** for review, and to COMIRB within their reporting guidelines according to their policies and procedures. The FDA will be notified by written report within 15 days of the Sponsor determining that the SAE or suspected adverse reaction meets FDA criteria for reporting.

Reporting mechanisms: AE forms will be completed and submitted on-line using the COMIRB AE reporting system. The report will include a description of the event, judgment as to whether or not it was related to study medication, and the outcome of the AE. All non-serious AEs, and those that are not unexpected or that are normal to the study medication, will be reported to the DSMB at the time in which the rest of data from an aggregate block of participants is submitted, or if the DSMB requests the information for their analysis in another trial-related matter.

Responsibility for preparing and submitting reports: The study coordinator will prepare the AE report and the PI or qualified sub-Investigator will review/edit as appropriate and the PI, study coordinator or other designated staff will submit the AE.

Confidentiality Procedures:

The meetings of the DSMB will be closed to respect the privacy of the research participants. Data will be kept in case report binders in a locked office when not in use. Data entered into the computerized data registry will only be accessible to those members of the research team.

9 Statistical, Data, and Other Considerations

